4.0 SELECTION AND ENROLLMENT OF PARTICIPANTS

4.1 Inclusion Criteria

Aim 1 (in-depth interviews): 40 HIV-negative men who have sex with men (MSM): must self-report: being assigned male sex at birth, HIV-negative, age 18 and above, ever having had anal sex with another man, currently reside in Guangzhou, China, identify as a Chinese citizen, able to being willing to sign written informed consent and participate in the study as procedures required.

Aim 2 (randomized controlled trial, RCT): 70 HIV-negative MSM: same characteristics as in Aim 1. AND, they must report:

- Having a smartphone with WeChat installed.
- Being assigned male sex at birth, HIV-negative, age 18 and above, ever having had anal sex with another man, currently reside in Guangzhou, China, identifying as a Chinese citizen, able to sign written informed consent and participate in the study as procedures require. AND
- Not currently using any medicine as PrEP
- At least one criterion associated with high risk of HIV infection in the past 6 months prior to enrollment as follows:
 - Unprotected (condomless) anal intercourse with male partner(s)
 - More than two male partners (regardless of condom use and HIV serostatus)
 - Reported STI, such as syphilis, HSV-2, gonorrhea, chlamydia, chancroid, or lymphogranuloma venereum.
 - Reported use of post-exposure prophylaxis (PEP)
 - Have a sexual partner living with HIV

4.2 Exclusion Criteria

Aim 1: Individuals who report any following status will be excluded from participating Aim 1:

- HIV-positive
- Mental health issues which may compromise participant adherence or safety, including memory loss, cognitive impairment, intellectual disability, or communication disorders.

Aim 2: Individuals who report any following status will be excluded from participating Aim 2

- HIV-positive
- Currently taking oral PrEP based on self-report
- Symptoms of acute HIV infection within the prior 30 days
- Contradictions to taking oral PrEP
- Personal diagnosis or family history of hemophilia Chronic Hepatitis B (self-report)
- Participating in another research study related to HIV and antiretroviral therapy or other intervention study
- Having serious chronic disease, including metabolic diseases (such as diabetes), neurological, and psychiatric disorders

- Mental health issues which may compromise participant adherence or safety, including memory loss, cognitive impairment, intellectual disability, or communication disorders.

4.3 Study Enrollment Procedures

Participant recruitment will be targeted to venues (health clinics, gay bar) and mediums (e.g. Internet, social media) that we have identified from past formative work to be frequented by MSM in Guangzhou, and specifically MSM who are seeking HIV testing or post-exposure prophylaxis.

Aim 1: Potential participants will be verbally screened for eligibility during their initial contact with the study team, before proceeding to the full informed consent and enrollment in in-depth interviews. All enrolled participants will be given a unique ID number for identification purposes.

Aim 2: Potential participants will be verbally screened for eligibility during their initial contact with the study team, before proceeding to the full informed consent and enrollment in the RCT. All enrolled participants will be given a unique ID number for identification purposes.

We will conduct a simple randomization that randomly assign the 70 participants to either the mini-app arm (n=40) or the control arm (n=30). Based on the timing of enrolling the study, each participant will be assigned a two-digit study ID (e.g., the first enrolled participant will be ID01; the second will be ID02; the last one enrolled will be ID70). Before enrollment, the study team will use the Microsoft Excel program to randomly assign the 70 IDs into group A (the intervention arm) and group B (the control arm). Once enrolled, a participant will be automatically assigned to either the intervention arm or the control arm based on his ID. If a participant quitted the study because of non-PrEP-related reasons (e.g., seroconversion, moving to other cities) after enrollment, we will recruit a new participant for replacement.

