Participants in both arms can choose to initiate PrEP at any time point since the initial visit until the end of 8th week. Participants can contact the study team via phone call, text messages or via the chat function in the mini-app to communicate their interest in PrEP initiation. If baseline assessment or follow-up survey results do not show contradictions to PrEP initiation, interested participants will be referred to the Department of Infectious Diseases at Guangzhou No.8 People's Hospital to consult a clinician regarding HIV risks and PrEP eligibility. As is standard of care for any patient starting PrEP, participants will take comprehensive physical examinations (including routine urine examinations, hepatic and renal function tests, blood glucose and lipids, and bone mineral density (BMD)). The study team will not have access to participants' medical records (i.e. the physical examination results). Participants who are confirmed by the clinician HIV-negative, with no serious liver or kidney dysfunction and negative for HBs antigen, without serology indicating osteoporosis, without clinical signs or symptoms consistent with acute viral

infection, will be prescribed either 8-week daily oral TDF/FTC or event-driven oral TDF/FTC based on participants' preference. The cost of physical examinations in order to get PrEP prescription will be covered by the study team. If a participant is eligible for starting PrEP and have been prescribed PrEP by a PrEP provider, the participant will get a 50% reimbursement of the cost for their first two months of PrEP doses (30 pills/month, up to 60 pills in total) filled at the in-house pharmacy of the study hospital (the Guangzhou Eighth People's Hospital).

Follow-up and Data collection

The active intervention period will last for 8 weeks, but participants in the intervention arm can have access to the mini-app throughout the whole study period or until the end of their first two-month PrEP use, which can be as long as 16 weeks. Baseline assessments will be conducted at the enrollment visit, with follow-up assessments conducted at 2, 4, 6, 8, 12 (post-intervention). Participants from both arms will need to complete a self-administrated Web-based survey at each assessment time point.

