7.0 PARTICIPANT WITHDRAW AND REPORT

Participants may voluntarily withdraw from the study for any reason at any time. No further data collection will occur from the date the decision is made to permanently discontinue the participant from the study. The study investigators also may withdraw participants from the study in order to protect participant or staff safety. Study staff will record the reasons for all withdrawals.

If a participant fails or is unable to comply with study procedures they will be withdrawn from the study. Participants will be withdrawn if they:

- are noticeably intoxicated or on illegal drugs.
- threaten a study staff member.
- are mentally handicapped and unable to give full informed consent.
- are incarcerated during course of study.
- become HIV-positive during course of study.
- reporting severe medication side effects after initiating PrEP and are advised to quit the study by a HIV specialist.

Any enrolled participant who report any of the above-mentioned events will be immediately stop participation in the study, and study staff will complete a Study Stop form for participants who are discontinued. This form will include the date, last research activity completed, and reason for study discontinuation. These will be reported to the UNC IRB and the Guangzhou No.8 People's Hospital IRB at the end of study.

Reporting is required of all unanticipated problems to the UNC IRB, including those which may occur after the participant has completed or has withdrawn from the study, including after study closure.

Unanticipated problems as defined by the UNC IRB:

Unanticipated problems involving risks to participants or others" or "Unanticipated Problem" refers to any incident, experience, or outcome that:

- is unexpected (in terms of nature, severity, or frequency) given (a) the research procedures that are described in the protocol-related documents, such as the IRB-approved research protocol and informed consent document; and (b) the characteristics of the participant population being studied;
- is related or possibly related to a participant's participation in the research; and
- suggests that the research places participants or others at a greater risk of harm (including physical, psychological, economic, or social harm) related to the research than was previously known or recognized.

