8.1 General Design

Aim 2 include a two-arm unblinded RCT, testing the efficacy of a mini-app-based PrEP intervention in promoting PrEP uptake among Chinese MSM compared to standard of care control.

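### Men who quit after allocation are replaced for loosely defined reasons that include seroconversion, and no stated rule keeps them in the analysis

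*Combined protocol and SAP*

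**What the plan says.** **Allocation (Section 4.3).** Seventy IDs are randomised to the two arms before enrolment, 40 to the mini-app and 30 to control. IDs are unique and follow enrolment order, and "the last one enrolled will be ID70". The arm follows from the ID: "Once enrolled, a participant will be automatically assigned to either the intervention arm or the control arm based on his ID".

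**Replacement (Section 4.3).** For a man who quits "because of non-PrEP-related reasons (e.g., seroconversion, moving to other cities) after enrollment, we will recruit a new participant for replacement".

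**Blinding (Section 8.1).** "Aim 2 include a two-arm unblinded RCT".

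**Withdrawal (Section 7.0).** "If a participant fails or is unable to comply with study procedures they will be withdrawn from the study". Becoming HIV-positive is also a listed ground for withdrawal. After that, "No further data collection will occur from the date the decision is made to permanently discontinue the participant from the study". The section adds: "Study staff will record the reasons for all withdrawals".

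**Outcome and analysis.** Section 6.3 defines the primary outcome as a number of men initiating PrEP within 8 weeks and gives no denominator. Section 8.2 names successful initiation as the endpoint. Section 8.6 gives chi-square tests, t-tests and logistic regression. None of the three states an analysis population, how withdrawn or replaced men are handled, or what is done when initiation status is unknown. Section 8.4 says the control arm is there so that an effect size can be estimated to power a full trial.

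**The concern.** Because the arm is set at enrolment, replacing a man after enrolment means replacing him after randomisation. Whoever judges that his reason was unrelated to PrEP can know his arm.

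One of the two named reasons bears directly on the outcome. Section 3.0 limits prescription to "Participants who are confirmed by the clinician HIV-negative" who also meet other conditions, so a man who seroconverts before starting PrEP can only be a non-initiator. Detection may also differ by arm. Only the intervention arm can order free HIV/syphilis kits through the mini-app (Sections 3.0 and 5.0), while controls receive recommendations and referrals to testing sites.

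If replaced men drop out of the denominator, non-initiators can be removed from one arm more than from the other. That would shift the estimate that Section 8.4 wants to carry forward. With no analysis set written down, the denominator can also be chosen after the results are seen.

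**Working it through.** **The plan's own figure.** 40 + 30 = 70, which agrees. Section 8.4 gives no power calculation, initiation rate or dropout allowance, so nothing else can be reproduced.

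**IDs.** If k men leave and recruitment restores 70 participants, 70 + k men are enrolled. IDs follow enrolment order and are unique, so a replacement takes the next unused ID and the arm already attached to it. The list covers 70 men, so k of the 70 + k fall beyond ID70, where neither ID nor arm is defined.

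**Bias model (assumptions, not document figures).** Let p be true initiation, equal in both arms (10, 20 or 30%). Let r be the share of an arm that leaves, and f the leavers' initiation rate relative to p. If leavers are left out, or replaced by men like those who stay, the expected rate in an arm is p(1 − f·r)/(1 − r). The bias is the intervention rate minus the control rate. Results are in percentage points.

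| Leavers (app v control) | f | p = 10% | p = 20% | p = 30% |
|---|---|---|---|---|
| 4/40 v 2/30 | 0 in both | 0.40 | 0.79 | 1.19 |
| 4/40 v 2/30 | 0.5 in both | 0.20 | 0.40 | 0.60 |
| 4/40 v 0/30 | 0 | 1.11 | 2.22 | 3.33 |
| 0/40 v 3/30 | 0 | −1.11 | −2.22 | −3.33 |
| 1/40 v 0/30 | 0 | 0.26 | 0.51 | 0.77 |
| 4/40 v 3/30 | 0 app, 1 control | 1.11 | 2.22 | 3.33 |

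Example for the first row at p = 10%: 0.10/0.90 − 0.10/0.9333 = 11.11% − 10.71% = 0.40 points.

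The bias is zero if f = 1 in both arms (leaving unrelated to initiation), or if r and f are both the same in the two arms. Equal leaving rates alone are not enough. In the last row 10% leave each arm, yet the bias is p/0.9 − p, the same as with 4 leavers v 0.

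**Against sampling error.** SE = √[p(1 − p)(1/40 + 1/30)] = 7.2, 9.7 and 11.1 points at p = 10, 20 and 30%. With f = 0, the uncorrected chi-square test at 5% rejects a true null in 4.8-5.4% of trials at 4 v 2, and in at most 6.1% at 4 v 0. With no leavers it rejects in 4.9-5.1%.

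**Unknown status.** This uses only the plan's arm sizes. Each man whose week-8 status stays unknown widens the best-to-worst-case range by 1/40 = 2.5 points in the app arm or 1/30 = 3.3 points in control. Four and two unknown give 4/40 + 2/30 = 16.7 points.

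**Cost of counting unknown as non-initiation.** The expected rate becomes p(1 − f·r). If loss is unrelated to initiation (f = 1), the bias is −p(r app − r control). That is −0.3 to −1.0 points at 4 v 2 and −1.0 to −3.0 at 4 v 0, where a complete-case analysis gives 0. If the unknown men did not initiate (f = 0), the non-initiation rule gives 0.

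**The case against.** The strongest reply is that this is a 70-man pilot, that the bias is a fraction of the standard error, and that the test's error rate hardly moves. That stands, and it limits the point to the missing rules. Seroconversion may also be too rare to matter: one such man in the app arm shifts the difference by 0.3-0.8 points. No document shows that leaving will differ by arm; the test-kit route is a plausible mechanism, not evidence.

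Three stronger readings are tempting and are not supported.

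- **That replaced men are excluded from the analysis.** Section 4.3 does not say so. It is silent, as are Sections 6.3, 8.2 and 8.6. Nor does Section 7.0 erase an initiation recorded before withdrawal; it stops further collection.
- **That a replacement has no defined ID or arm at all.** Enrolment-order, unique IDs imply the next unused ID and its arm, which also argues against reuse of the vacated ID. The gap opens once ID70 is used.
- **That the trial's result would be badly distorted.** The direction can go either way and the size is modest under the assumptions tried. The opposite inference, that balanced attrition makes replacement harmless, fails as well.

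The Aim 2 flowchart (Figure 2) is not visible, so the silence described here is that of the readable text.

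**Conclusion.** The concern holds, as a rule that should be fixed and not as a demonstrated large bias. As written, Section 4.3 permits outcome-related replacement after randomisation, in an unblinded trial, on a criterion left to judgement, and no visible text keeps the replaced man in the comparison. That conclusion rests on the wording alone and is firm.

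The size is not firm. It depends on assumed leaver counts, 10-30% initiation, no true effect and leavers who never initiate. Under these the shift is 0.4-1.2 points at 4 v 2 and 1.1-3.3 at 4 v 0, and it reverses if more controls leave. The practical harm is an effect size for the full trial whose denominator was never fixed, with no means for a reader to see what replacement did to it.

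**What to change.** **Section 4.3.** State that every randomised man is analysed in his assigned arm. Any extra recruit is added to, not substituted for, the man who left, and takes the next unused ID. After ID70, IDs come from an extension list randomised in advance in the same 4:3 ratio. Accept that the final split may differ from 40/30.

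**Section 7.0.** Separate stopping study activities from stopping outcome follow-up. Unless consent is withdrawn, seek week-8 initiation status by the existing web survey or from the study's own reimbursement records. A reimbursement shows that PrEP was filled. Its absence does not prove non-initiation, because it covers only the study hospital's pharmacy and the team cannot see medical records.

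**Section 8.6.**
- Count initiation recorded before withdrawal.
- Count a man confirmed HIV-positive before starting PrEP as a non-initiator.
- Count status still unknown as non-initiation in the primary analysis, with complete-case and best/worst-case results as sensitivity analyses.
- Report withdrawals by arm and reason.

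**Cost.** The change needs a protocol amendment with IRB approval and possibly a revised consent form (Section 9.2.6), a little more follow-up, and perhaps more than 70 men. Stated uptake will be slightly lower. The non-initiation rule is itself biased if loss is unequal and unrelated to initiation (−0.3 to −1.0 points at 4 v 2), which is why the sensitivity analyses are needed. Some men who quit will not respond, so some status will stay unknown. Reasons for withdrawal are already recorded, so tabulating them by arm costs almost nothing.

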5.0 STUDY TREATMENT (OR INTERVENTION)

Aim 1: No study treatment or intervention.

Aim 2: Participants will receive two types of study treatment:

(1) Standard of Care

During their initial visit at Guangzhou No.8 People's Hospital (in-person or via videoconferencing systems), after enrollment, participants from both arms will receive written HIV prevention materials (hard-copy at the study clinic or electronic files) including basic facts of PrEP, recommendations for HIV/STIs testing and referrals to local HIV/STIs testing sites and prevention services.

(2) The Mini-app Intervention

In addition to the standard of care, participants who are assigned to the intervention arm will receive a mini-app-based PrEP intervention for up to 16 weeks. The intervention tool is a mini-app that is built in a popular Chinese social media mobile platform, WeChat, to increase the engagement for PrEP education and PrEP initiation among Chinese MSM.

Right after enrollment, participants randomized to the intervention arm will be guided by study staff through the mini-app access process and given a tour to highlight features. A prototype of the mini-app has been developed from an MSM-friendly doctor finder hackathon contest (April 2019, Guangzhou) by a team of Chinese young MSM. The mini-app will be refined in terms of prioritized topics, graphical designs and tones of language based on results from Aim 1 before starting trial in Aim 2. The overall goal of the mini-app is for PrEP education. It has four main functions: (1) a mini-classroom that contains a series of HIV-, sexual health-, and PrEP-related educational articles in Chinese; (2) an HIV/syphilis self-test toolkit ordering system that allows users to order a finger-prick HIV rapid test toolkit and shipped to home for free (one piece at a time); (3) an asynchronous message function that allows users to chat with a trained PrEP counselor; and (4) a user profile page where users can manage all HIV test orders. The mini-app wireframe is presented in Figure 3.

[figure not shown]

Figure 3. Wireframe of the mini-app PrEP intervention (Aim 2)

Participants in the intervention arm will have access to the mini-app for up to 16 weeks since enrollment. Usage of the mini-app will at participants' own discretion or preference. A one-sentence weekly reminders that encourage participants to use the mini-app will be sent out through text messages. The mini-app will not be able to track any individual user information or user activity within the mini-app. Self-reported app usage will be assessed in bi-weekly follow-up

surveys and in-depth interviews. At 8th week, participants in the intervention arm will be allowed to continue using the mini-app, but will no longer receive reminder messages.

6.0 DATA COLLECTION

6.1 Data collection activities

Data collection activities will be described by study aims.

Aim 1: Qualitative interviews

One-on-one in-depth interviews will be conducted in multiple settings in Guangzhou, China including an HIV testing clinic, and private locations of the participants' choosing (e.g. private room in a tea shop, private office space). Each interview will last 60-90 minutes. Interviews will be audio taped, transcribed verbatim in Chinese, summarized in English for analysis. During the interview participants will also be required to complete a 5-point Likert usability scale and a brief demographic survey.

Due to the social distancing requirement during the COVID-19 pandemic as well as to reduce health risks for both participants and research staff, in-depth interviews may be conducted via videoconferencing system (e.g., Zoom, WeChat video/audio call) depending on the participant's preference.

Aim 2: Two-arm RCT

Data collection in Aim 2 include Web-based baseline and follow-up assessment surveys, and qualitative interviews.

Web-based surveys

Baseline assessment will be conducted at the initial enrollment visit, with follow-up assessments conducted at 2, 4, 6, 8, and 12 weeks. All Web-based survey will be self-administrated and collected through a Chinese professional secure electronic survey platform (www.wjx.cn). Survey links will be sent to participants via text message that participants can choose to finish the survey on their phone or computer.

Qualitative interview

Similar to in-depth interviews in Aim 1, in-depth interviews in Aim 2 will be conducted in multiple settings in Guangzhou, China including an HIV testing clinic, and private locations of the participants' choosing (e.g. private room in a tea shop, private office space).

Due to the social distancing requirement during the COVID-19 pandemic as well as to reduce health risks for both participants and research staff, in-depth interviews and enrollment visit may

be conducted via videoconferencing system (e.g., Zoom, WeChat video/audio call) depending on the participant's preference.

6.2 Data Management

Only authorized users (PIs, faculty advisor), based on correct login will be able to access and open the study surveys and in-depth interview recordings and transcripts. In-depth interviews will be audio taped, transcribed verbatim (in Chinese), summarized in English and organized and managed using Dedoose cloud-based qualitative data analysis software (www.dedoose.com). Web-based survey will be collected through a Chinese professional secure electronic survey platform Wenjuanxing (www.wjx.cn). Survey data will be downloaded from Wenjuanxing and will be stored on password protected encrypted study computers along with other electronic study files. All study files will have a back-up copy stored on UNC secure server space that only study personnel will have access to. All information will be kept confidential, with responses labeled by an identification number available only to investigators in locked or password secured files.

